## 1. What the study will do

This study responds to Request for Application-DA-19-035, HEAL (Helping End Addiction Long Term) initiative: Preventing OUD in Older Adolescents and Young Adults (ages 16-30) by developing and implementing a culturally centered intervention to address opioid use among urban American Indian/Alaska Native (AI/AN) emerging adults. The primary goal of this behavioral study is to compare AI/AN emerging adults who receive TACUNA (Traditions and Connections for Urban Native Americans) plus a Wellness Circle (WC) to those AI/AN emerging adults who receive an opioid education workshop on outcomes (e.g., opioid misuse and alcohol and other drug use) over a period of 12 months.

- TACUNA will be a virtual motivational interviewing group intervention that incorporates traditional practices and discussion of how to cultivate healthy social networks and cultural worlds. The Wellness Circle will be for emerging adults and people in their social network and will focus on how social networks and cultural connectedness influence healthy behaviors.
- Opioid education (control) will focus on discussion of opioid misuse within the AI/AN urban community and ways to reduce use in a culturally appropriate manner.

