### Phase 2/UH3

Note: Due to the COVID-19 pandemic and restrictions on social gatherings, this study pivoted from in-person group implementation to virtual group implementation. This allowed us to expand participation beyond our original urban sites in California as we were no longer limited by facilitating in-person groups.

In Native American research, it is typical that intervention and control groups receive some degree of an intervention. We will enroll 370 participants at baseline across the United States who we determine represent the broader population of 18-25 year old urban AI/AN emerging adults. In a randomized controlled trial—an unmasked, 2-arm parallel intervention model—participants either will be assigned to TACUNA (n = 185), which comprises three virtual workshops utilizing motivational interviewing, social network visualization, and integrating traditional practices and a Wellness Circle (WC), or to one virtual culturally sensitive opioid education workshop (n = 185). WCs will be culturally focused, and feature Native foods and entertainment (e.g., Native lectures, storytellers, cooking demonstrations, and sage ceremony).

**Aim 2.** We will compare AI/AN EAs who receive TACUNA+WC to AI/AN EAs who receive opioid education. We will compare outcomes at 3, 6, and 12-months to determine (a) whether changes occur in initiation and escalation of opioid use and alcohol and other drug use, such as cannabis, and related consequences; time spent around peers who use opioids and AOD, and perceived prevalence of peer use, (b) whether clinically significant changes occur in physical, social, emotional, and functional well-being, as well as spirituality and cultural connectedness, and (c) if reductions occur, estimate effect sizes.

**Aim 3.** We will explore potential mechanisms of change for decreases in opioid and AOD use outcomes through mediation analyses, including changes in social networks and cultural connectedness.

**Aim 4.** We will develop and test strategies to facilitate sustainability of TACUNA within these communities through key informant interviews upon conclusion of the randomized controlled trial.

**Aim 5.** We will conduct an economic evaluation to quantify programmatic costs and cost-effectiveness of the multi-tiered intervention approach, relative to opioid education.

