## 1. Statistical aspects of the clinical trial design

**Aim 2.** We will compare outcomes at 3-, 6- and 12-months for AI/AN EAs who receive opioid education (n=185) to AI/AN EAs who receive TACUNA+WC (n=185).

**Aim 3.** We will conduct mediation analyses to examine whether changes in social networks and cultural connectedness serve as explanatory mechanisms for reductions in opioid and AOD use.

**Aim 4. Sustainability.** We will develop and test strategies to facilitate sustainability of TACUNA within these communities through 20 key informant interviews.

**Aim 5. Economic evaluation.** We will follow recommendations from the Panel of Cost-Effectiveness in Health and Medicine, by reporting costs and cost-effectiveness estimates in terms of two reference cases, one based on a program perspective (programmatic and provider time costs) and the other on a societal perspective that incorporates a broader range of costs, such as opportunity costs to participants.

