*Costs.* We will account for programmatic costs following the micro-costing approach of prior work. Intervention costs will be obtained from several sources, including program records and primary collection of cost and time use data. Programmatic input costs include labor (including overhead), materials, and other costs of implementing the intervention; for the societal perspective, we will also consider (a) transportation costs to participants; (b) opportunity costs of EAs; and (c) space and utility costs. The analysis will exclude research costs, although we can incorporate these in sensitivity analyses.

*Effectiveness.* We will follow recommendations for economic evaluations of AOD use interventions and consider multiple outcomes from Aim 2 analyses to compare effectiveness at 6 and 12 months after baseline. Our primary effectiveness measures will be abstention from opioid misuse in the past 3 months (either through preventing initiation or discontinuing use); abstention or consumption below the threshold of heavy use for alcohol and cannabis; and a reduction in time spent around peers who misuse opioids. Given our focus on prevention, an effectiveness outcome related to peers will be informative.

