*Economic analysis.* We will conduct an intent-to-treat analysis, aligned with the primary analytic plan of Aim 2. We will first perform deterministic analyses (i.e., direct calculations) to sum program costs (and opportunity costs for the societal perspective), yielding incremental net costs as the difference between net costs per participant to (a) those receiving TACUNA+WC and (b) those receiving opioid education. Total costs and costs per participant will be calculated separately by site to assess whether key factors determine cost variability for each intervention. Next, we will perform probabilistic (Monte Carlo) analyses to account for uncertainty and variability in cost parameters. Incorporating Aim 2 findings for each of our primary effectiveness outcomes, we will construct short term incremental cost-effectiveness ratios (ICERs) for each outcome. We will assess model and parameter uncertainty on each outcome's effect sizes, allowing us to consider a range of values from findings related to uncertainty or variability in the relative effectiveness of TACUNA+WC compared to opioid education. We will construct ICER confidence intervals using nonparametric bootstrapping techniques within the multivariable framework, although we may consider other methods.

*Sensitivity analysis.* We will perform sensitivity analyses to test the importance of key model parameters, such as the price of a given resource, on ICER findings. Additionally, we will consider how costs and cost-effectiveness differ under alternative parameter assumptions as well as under different assumptions about attendance.

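### The societal cost list counts only the emerging adults' time, although the Wellness Circle, held in the TACUNA arm alone, also takes the time of people from their social networks

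*Combined protocol and SAP*

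**What the plan says.** SAP section 1, Aim 5, plans two reference cases. One takes the program's perspective. The other is a "societal perspective that incorporates a broader range of costs, such as opportunity costs to participants".

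SAP section 4, Aim 5 (Costs), itemizes what the societal case adds to programmatic inputs: "we will also consider (a) transportation costs to participants; (b) opportunity costs of EAs; and (c) space and utility costs". The same paragraph mentions collecting cost and time-use data but does not say whose time.

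Protocol section 1 describes who attends the added component: "The Wellness Circle will be for emerging adults and people in their social network". Protocol section 2 (Phase 2/UH3) gives the TACUNA arm three virtual workshops and a Wellness Circle. The control arm gets one virtual opioid education workshop, with no guests described. Each arm has 185 participants.

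The Economic analysis paragraph sums program costs, plus opportunity costs for the societal case, "yielding incremental net costs as the difference between net costs per participant" in the two arms. It then builds an ICER for each primary effectiveness outcome.

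**The concern.** Item (b) reaches the EAs, the term the plan uses under Aim 2 for the people being compared. Network members who come to a Wellness Circle give up time in the same way, and their presence is part of the intervention by design. No item on the list covers that time.

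The gap is not shared between the arms. A cost left out of both arms equally would cancel in the difference, but this one arises only under TACUNA+WC and so passes straight into the incremental cost. Virtual delivery does not remove it, because joining online still takes time.

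At stake are the societal incremental cost and each societal ICER built on it. Guest time is not a programmatic cost, so the program-perspective ICERs do not change. Nor does any Aim 2 comparison.

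**Working it through.** The documents state no cost, unit price, guest count, session length or ICER, so there is no figure of the plan's own to reproduce. The direction follows from algebra. The size can only be illustrated.

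**Direction**
- ICER = (C_T − C_C) / (E_T − E_C) = ΔC / ΔE, where T is TACUNA+WC and C is opioid education.
- Let G > 0 be guest time cost per TACUNA participant. The control arm has none.
- Counted increment = true ΔC − G, so the incremental cost is too low by G whatever the effect.
- If ΔE > 0, the ICER is too low by G/ΔE. If ΔE is zero or negative, that statement about the ICER does not follow.

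**Share of incremental attendance time**
- From protocol section 2: TACUNA sessions = 3 workshops + 1 Wellness Circle = 4; control sessions = 1.
- Assumed: equal session lengths, full attendance, equal value of time for guests and EAs, one Wellness Circle per participant, and g guests per participant.
- Counted increment = 4 − 1 = 3 session-units. Increment with guests = 3 + g. Omitted share = g/(3 + g).

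| g (assumed) | 3 + g | Omitted share of attendance time | Guest sessions over 185 participants |
|---|---|---|---|
| 0.25 | 3.25 | 7.7% | 46.25 |
| 0.5 | 3.5 | 14.3% | 92.5 |
| 1 | 4 | 25% | 185 |
| 2 | 5 | 40% | 370 |
| 3 | 6 | 50% | 555 |

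**From attendance time to total cost**
- Let s be the part of the counted societal increment that is EA attendance time. One session-unit is then s/3 of that increment, and guest time adds g·s/3.
- Omitted share of the total = (g·s/3) / (1 + g·s/3) = g·s/(3 + g·s).
- This equals g/(3 + g) only if s = 1. Labor, overhead and materials also enter the increment. If those other components add to it, s is below 1 and the share of the total is smaller. The documents do not give s.

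**Money, under assumed values (guests × hours × hourly value, in currency units)**
- Low: 0.5 × 1 × 10 = 5 per participant; 5 × 185 = 925 for the arm.
- High: 3 × 3 × 30 = 270 per participant; 270 × 185 = 49,950 for the arm.
- With an assumed gain in abstention of 10 percentage points, the ICER would rise by 5/0.10 = 50 to 270/0.10 = 2,700 per additional abstainer. So wide a range shows that the size cannot be settled from the documents.

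**The case against.** **The cost boundary is open.** SAP section 1 introduces participants' opportunity costs as an example, section 4 says the items will be considered rather than that they are the only ones, and the time-use collection is not restricted to EAs. An analyst could therefore add guest time without breaching the plan. That stands as a reason to call this a gap in the written rule, not a forecast of what the team will do. It does not remove the gap: both places that name whose opportunity cost is counted name only participants or EAs.

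**The sensitivity analysis could absorb it.** The plan says "we will consider how costs and cost-effectiveness differ under alternative parameter assumptions as well as under different assumptions about attendance". Varying attendance changes the quantity of items already in the cost model. It does not add an item that is missing, and guest time is not named there.

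**Guest benefits are left out too.** A reader might infer that the omission tilts the whole societal comparison towards TACUNA. The documents do not support that. The effectiveness measures come from Aim 2 outcomes, so any benefit to network members also lies outside the boundary, and its size is unknown. What stands is narrower: for the plan's own participant-based outcomes, the cost side is too low. An uncounted benefit does not correct a cost total, but it should be disclosed beside it.

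**The cost may be small.** It may be. Mean guest attendance below one per participant is plausible, and labor could dominate the increment.

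**Conclusion.** The point holds for the societal reference case only. Followed as written, the plan understates the societal incremental cost of TACUNA+WC for any guest attendance above zero. It understates the societal ICER if TACUNA's incremental effect is positive.

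The size is not known. The range of about 8% to 50% for 0.25 to 3 guests per participant is a share of incremental attendance time and rests on the four assumptions set out above. A reader might take it as the error in the ICER itself, but the documents give no cost breakdown that would allow that. Nor do they give figures showing that the listed transport and space items are negligible under virtual delivery, so the point does not rest on that contrast.

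This should be corrected before the economic analysis, since it is a one-directional gap in a stated costing rule and is cheap to close. It has no bearing on the trial's efficacy conclusions.

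**What to change.** - In SAP section 4, Aim 5 (Costs), change item (b) to: *opportunity costs of EAs and of social-network members attending the Wellness Circle*, with both valued by the same method.
- Take the number of guests at each Wellness Circle from program records, which the plan already names as a cost source. The documents do not say that guest attendance is recorded. If no counts exist, vary guests per participant over a stated range in the planned sensitivity analysis.
- Report the societal incremental cost and ICER with and without guest time.
- State that benefits to guests are not counted in the effectiveness measures.

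The cost is a phrase in the SAP, a head count per Wellness Circle and one extra line of results. The societal ICER will look somewhat less favourable to TACUNA if its incremental effect is positive. Design, sample size and intervention do not change.

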## 5. Planned presentation of results in formats such as tables, listings, and figures

Results will be depicted in tables or figures as appropriate.

## 6. Plans for interim and final analysis and statistical analysis of the primary and secondary variables and other data

All analyses detailed above in Section 3 including timepoint specific follow-up as well as overall longitudinal models will compare intervention conditions on change in primary outcomes. Mediation models will include secondary variables (social networks and cultural connectedness) as potential explanatory mechanisms of change.
